9.4.4. Safety Analyses

The assessment of safety will be based mainly on the frequency of adverse events based on the Common Terminology Criteria for Adverse Events (CTCAE version 4) grade. Adverse events will be coded according to MedDRA, current version. The safety outcomes will include the occurrence of at least one serious adverse event, of at least one grade 3/4 adverse event, and of at least one adverse event requiring the discontinuation of study treatment.

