7.3.3. Treatment Phase

Treatment dosing continues for at least 6 months (i.e. a minimum of 12 cycles) until disease progression (radiological) or a criterion for removal from study are reached. Every cycle will be allowed window of +/- 24 hours.

All patients, on both arms, will complete radiology scans for RECIST evaluation every 8 weeks (+/- 7 days). Radiology will be assessed using triphase contrast CT of the chest, abdomen and pelvis. MRI assessments of tumor status may replace CT scans if needed. Serum levels of tumor marker CA19-9 and performance status also will be assessed every 8 weeks.

Chemotherapy breaks, of 3 weeks or less only, for patient emergencies are allowed and must be

documented.

CYCLE: 2 (Day 15 – Day 29):

1. **Adverse Event Assessment:** record adverse events as reported by participant or observed by investigator
2. **Pre-dosing Tests:** Clinical hematology (including coagulation) and chemistry tests as well as PRO has to be done at this cycle
3. **Administration of Study Treatment:** same as Cycle 1
4. **Sparse PK sampling** (see Sparse PK sampling schedule in Section 7.1.1, Table 13)
5. **Sparse ECG** (see Sparse ECG measurement schedule in Section 7.1.1, Table 15)

CYCLE: 3 (Day 30 – Day 44):

1. **Adverse Event Assessment:** record adverse events as reported by participant or observed by investigator
2. **Pre-dosing Tests:** Clinical hematology (including coagulation) and chemistry tests
3. **Administration of Study Treatment:** same as Cycle 1
4. **Sparse PK sampling** (see Sparse PK sampling schedule in Section 7.1.1, Table 13)
5. **Sparse ECG** (see Sparse ECG measurement schedule in Section 7.1.1, Table 15)

CYCLE: 4 (Day 45 – Day 59):

1. **Adverse Event Assessment:** record adverse events as reported by participant or observed by investigator
2. **Pre-dosing Tests:** Clinical hematology (including coagulation) and chemistry tests as well as PRO has to be done at this cycle
3. **Administration of Study Treatment:** same as Cycle 1
4. **Observations after the Intervention:** radiology scan for the measurement of ORR (approximate, all scans will be done every 8 weeks, +/-7 days), CA19-9, and optional blood draw
5. **Sparse PK sampling** (see Sparse PK sampling schedule in Section 7.1.1, Table 13)

CYCLE: 5 (Day 60 – Day 74):

1. **Adverse Event Assessment:** record adverse events as reported by participant or observed by investigator

2. **Pre-dosing Tests:** Clinical hematology (including coagulation) and chemistry tests

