8.3. Time Period and Frequency for Event Assessment and Follow-Up

The occurrence of an AE or SAE may come to the attention of study personnel during study visits and interviews of a study participant presenting for medical care, or upon review by a study monitor. All AEs including local and systemic reactions not meeting the criteria for SAEs will be captured in the CRF. Information to be collected includes event description, time of onset, clinician's assessment of severity, relationship to study product (assessed only by those with the training and authority to make a diagnosis), and time of resolution/stabilization of the event. All AEs occurring while on study must be documented appropriately regardless of relationship, action taken with study drug (drug withdrawn, dose reduced), other treatment for AE (drug therapy, other procedure) and outcome of AE. All AEs will be followed to adequate resolution (return to baseline).

Any medical condition that is present at the time that the participant is screened will be considered as baseline and not reported as an AE. However, if the study participant's condition deteriorates at any time during the study, it will be recorded as an AE. UPs will be recorded in the data collection system throughout the study.

Changes in the severity of an AE will be documented to allow an assessment of the duration of the event at each level of severity to be performed. AEs characterized as intermittent require documentation of onset and duration of each episode. Disease progression will not be considered as an AE/SAE.

The PI will record all reportable events with start dates occurring any time after informed

consent is obtained until 7 (for non-serious AEs) or 30 days (for SAEs) after the last dose of the study drug. At each study visit, the investigator will inquire about the occurrence of AE/SAEs since the last visit. Events will be followed for outcome information until resolution or stabilization.

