9.5. Sample Size

Approximately 500 patients will be entered in the trial. This number accounts for ineligible and unevaluable patients, as well as for dropouts.

The sample size calculation is based on the following expected benefits of the experimental treatment (devimistat + mFFX) over the control treatment (FFX):

- a 30% reduction in the risk of death from any cause; specifically, median OS is assumed equal to 12 months in the control arm vs. 17.14 months in the experimental arm, i.e. an OS hazard ratio equal to 0.7. For a power of 90% and a type-1 error level of 0.025, 335 deaths need to be observed. .
- a 30% reduction in the risk of tumor progression or death from any cause; specifically, median PFS is assumed equal to 6.4 months in the control arm vs. 9.14 months in the experimental arm, i.e. a PFS hazard ratio equal to 0.7. For a power of 90% and a type-I error level of 0.025, 330 PFS events need to be observed.

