6.3.3 Safety Analyses

The assessment of safety will be based mainly on the frequency of adverse events based on the Cancer Therapy Evaluation Program (CTEP) Active Version of the NCI Common Terminology Criteria for Adverse Events (CTCAE 4.0) grade. The CTEP Active Version of the CTCAE is identified and located on the [CTEP website](#). If the severity or intensity is not specifically graded by the guidance document from CTEP, the site investigators have been instructed in the protocol to revert to the general definitions of grade 1 through grade 5 shown in the table below. Additional information about adverse event or unanticipated problem reporting can be found in the protocol, section 8.

Severity	Description
Grade 1	Mild; events require minimal or no treatment and do not interfere with the participant's daily activities.
Grade 2	Moderate; events result in a low level of inconvenience or concern with the therapeutic measures. Moderate events may cause some interference with functioning.
Grade 3	Severe; events interrupt a participant's usual daily activity and may require systemic drug therapy or other treatment.
Grade 4	Life threatening or disabling; patient at risk of death at the time of the event.

Confidential

Grade 5	Death related to AE.
---------	----------------------

The following tabular summaries of adverse events will be provided using the safety population:

- All AEs by SOC and CTCAE term, by treatment arm and overall
- Patients with at least one AE by SOC and CTCAE term, by treatment arm and overall
- Patients with at least one AE by relatedness, by treatment arm and overall
- Patients with at least one AE by severity, by treatment arm and overall
- All serious AEs (SAEs) by SOC and CTCAE term, by treatment arm and overall
- Patients with at least one SAE by SOC and CTCAE term, by treatment arm and overall
- Patients with at least one AE that led to a change in study medication (e.g., dose modification, interruption, or permanent discontinuation), by treatment arm and overall
- Patients with at least one AE requiring a change in concomitant therapy (e.g., addition, interruption, discontinuation, or change in a concomitant medication, therapy, or treatment), by treatment arm and overall.

Adverse events that are still ongoing at the time of data cut-off should not be included in any of the tables described above. Instead, a separate table should be presented containing all on-going AEs by SOC and CTCAE term, by treatment arm and overall.

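### The planned adverse event tables compare arms only by crude counts, although recording stops soon after the last dose and the plan expects longer treatment in Arm 1, so toxicity and length of observation are mixed

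*Protocol*

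**What the plan says.** Safety of devimistat plus mFFX versus FFX is a comparative secondary objective (Protocol synopsis; SAP 3.1.2).

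- **Measure.** Protocol 9.4.4: "The assessment of safety will be based mainly on the frequency of adverse events". Its named outcomes are per-patient yes/no outcomes: "the occurrence of at least one serious adverse event, of at least one grade 3/4 adverse event", and at least one AE that led to stopping treatment.
- **Tables.** SAP 6.3.3 lists eight tables of events or patients, for example "Patients with at least one AE by SOC and CTCAE term, by treatment arm and overall". None has time at risk as a denominator.
- **Recording window.** Protocol 8.3 collects events "until 7 (for non-serious AEs) or 30 days (for SAEs) after the last dose of the study drug".
- **Treatment duration.** Protocol 7.3.3: treatment continues "until disease progression (radiological) or a criterion for removal from study are reached", in both arms.
- **Expected durations.** Protocol 9.5: "median PFS is assumed equal to 6.4 months in the control arm vs. 9.14 months in the experimental arm".
- **Exposure.** SAP 5.5 plans an exposure table by arm, and SAP 7.1 summarises treatment status and discontinuation by cycle. Neither enters an AE comparison. Neither document describes a rate per unit time, a time-to-first-event analysis or an AE table by cycle.

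**The concern.** Because recording is tied to the last dose, a patient is observed for AEs for about as long as he or she is treated. If the efficacy assumption is right, Arm 1 patients stay on treatment longer and have more time to record a first event. Crude proportions would then be higher in Arm 1 even if monthly toxicity were identical. If Arm 1 patients stop earlier, the distortion reverses and could hide real toxicity.

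The protocol's background (2.1.2) argues for first-line therapy with less toxicity, and the backbone doses differ by arm. The AE comparison will therefore be read as evidence on relative toxicity, and the planned tables cannot separate toxicity from duration.

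**Working it through.** **1. The plan's own figure.** Protocol 9.5: "For a power of 90% and a type-I error level of 0.025, 330 PFS events need to be observed", at a hazard ratio of 0.7 with 1:1 allocation. Schoenfeld: 4 × (1.960 + 1.2816)² / (ln 0.7)² = 42.03 / 0.1272 = 330.4, which agrees with 330. Also 6.4 / 0.7 = 9.14, and 9.14 / 6.4 = 1.428, so the assumed median is 43% longer in Arm 1.

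**2. Events that keep accruing.** Assumptions (mine, not the plan's): treatment lasts to progression; treatment times are exponential at the plan's medians; the first-event hazard λ is constant and equal in both arms.

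- μ = ln 2 / median = 0.1083 (control) and 0.0758 (Arm 1) per month.
- With a recording lag of L months after the last dose, P = 1 − [μ/(μ+λ)] × exp(−λL). With L = 0 this is λ/(λ+μ).
- λ is solved from the chosen control incidence. For 50% and L = 0, λ = 0.1083, so Arm 1 has 0.1083 / (0.1083 + 0.0758) = 58.8%.

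**3. With a data cut-off.** Protocol 9.4.6 foresees accrual over 33 months, and SAP 5.1.1 places the analysis about 33 months after accrual starts. With uniform accrual (assumed), potential follow-up is uniform on 0 to 33 months.

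- Mean treatment time is (1/μ) × [1 − (1 − exp(−33μ))/(33μ)] = 6.7 versus 8.3 months, a ratio of 1.24.
- With s = λ + μ and L = 0, P = (λ/s) × [1 − (1 − exp(−33s))/(33s)].

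Arm 1 incidence at equal monthly toxicity:

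| Control | No lag | 7-day lag | 30-day lag | 33-month cut-off, no lag |
|---|---|---|---|---|
| 10% | 13.7% | 13.6% | 13.4% | not run |
| 30% | 38.0% | 37.8% | 37.3% | 35.3% |
| 50% | 58.8% | 58.6% | 58.1% | 56.3% |
| 70% | 76.9% | 76.8% | 76.4% | 75.2% |
| 90% | 92.8% | 92.7% | 92.6% | 92.1% |

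If only half of the 43% becomes extra treatment time (30-day lag, no cut-off), 50% becomes 54.4%.

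**4. Early-onset events.** If the hazard acts only in the first K months on treatment, P = (λ/s) × [1 − exp(−sK)]. A control incidence of 50% becomes 50.7% (K = 1), 51.4% (K = 2) or 52.0% (K = 3). Over control incidences of 30% to 70% the gap is 0.5 to 2.5 points.

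**5. Would an adjusted measure do better on its own?**

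- *Pooled exposure-adjusted rate* (first events over time to first event or end of treatment). With a constant hazard the rate ratio is 1.00. For early-onset events, time at risk is (1 − exp(−sK))/s + exp(−sK)/μ. At 50% control incidence and K = 1 to 3, the Arm 1/control ratio is 0.72 to 0.76, although the hazards are identical.
- *Cumulative incidence with end of treatment as a competing event*: (λ/s) × [1 − exp(−st)]. At 24 weeks (168 / 30.4375 = 5.52 months) the 50% case gives 34.9% versus 37.5%, and the 70% case 60.5% versus 64.4%. The residual gap over the 30% to 70% cases is 1.4 to 3.9 points at 24 weeks and under 2 points at 12 weeks.

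**The case against.** **The hazard is not constant.** Protocol 6.1.6 reduces or stops backbone drugs stepwise with no re-escalation, and oxaliplatin may be dropped after cycle 12. Twelve 14-day cycles last 168 days, about 5.5 months, so the time between the two assumed medians falls after that point. This stands, and it is why the size depends on event type. It does not remove the concern: Appendix III reports that sensory neuropathy, seen in 17 of 18 patients (94%), came on late, and late events are the ones that unequal exposure affects most.

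**Treatment time need not follow PFS.** Protocol 5.3.1 lists many other reasons for stopping. This also stands; the half pass-through case shows a smaller gap.

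**Readers can already see exposure.** SAP 5.5 and 7.1 show whether exposure differs, but not how the AE comparison changes because of it.

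**Crude incidence is a legitimate quantity.** The chance of an event over the regimen as given is clinically meaningful and is not biased for that question. This is a reason to keep the crude tables.

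**A reader might infer more than the documents support:**

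- *That the gap gives a false-positive rate for safety.* The safety sections specify tabulations only, and safety is outside the testing hierarchy (Protocol 9.4.2; SAP 5.4). The general sentence on stratified tests for binary outcomes is not tied to the AE tables.
- *That the tables are biased against devimistat overall.* The direction depends on which arm is treated longer. SAP 6.3.3 also leaves events ongoing at cut-off out of its main tables. That is a separate matter, but it could offset part of an Arm 1 excess.
- *That an exposure-adjusted rate should become the comparison.* Step 5 shows that it can create an apparent 24% to 28% advantage for Arm 1 when events come early.

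**Conclusion.** The concern holds as a gap in SAP 6.3.3: the only planned between-arm AE summaries are crude counts, and these mix toxicity with length of observation.

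At equal monthly toxicity and the plan's PFS medians, the artefact is about 5 to 9 points for accruing events at control incidences of 30% to 70%. The lower part of that range, 5 to 6 points, comes from uniform accrual and a 33-month cut-off. It is about 1 to 2 points for events limited to the first 1 to 3 months, and under 3 points at 90% incidence. These sizes rest on exponential treatment times that follow PFS. True monthly rates by arm are unknown, so the figures illustrate scale and do not predict a result.

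Because the size differs by event type, a reader cannot correct the crude tables by eye. No single adjusted measure is safe alone either. The change is a cheap improvement to interpretation and does not affect the primary analysis.

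**What to change.** In SAP 6.3.3, keep all crude tables and add supplementary summaries by arm for grade 3 or higher AEs, SAEs and AEs leading to discontinuation:

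- **(a)** The exposure-adjusted incidence rate per 100 patient-months at risk, with time at risk ending at the first event or at the 7- or 30-day limit. Report it by treatment period (for example cycles 1–6, 7–12 and beyond 12), because hazards are unlikely to be constant.
- **(b)** The cumulative incidence of first event at 12 and 24 weeks. State how death and end of treatment are handled, since treating end of treatment as a competing event leaves a small residual gap.

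Add a sentence that crude frequencies are to be read alongside these summaries and the SAP 5.5 exposure table. Do not replace the crude comparison with the exposure-adjusted rate.

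Cost: a few SAP lines before database lock and one or two extra tables. The inputs (event onset, first and last dose, and death dates) are already collected.

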8.1.2. Definition of Serious Adverse Events (SAE)

An AE or suspected adverse reaction is considered "serious" if, in the view of either the investigator or sponsor, it results in any of the following outcomes:

- Results in death
- Is life-threatening
- Requires hospitalization (initial or prolonged)
- Results in persistent or significant disability/ incapacity
- Is a congenital anomaly/birth defect
- Is otherwise considered as medically important

Important medical events that may not result in death, be life-threatening, or require hospitalization may be considered serious when, based upon appropriate medical judgment, they may jeopardize the patient or subject and may require medical or surgical intervention to prevent one of the outcomes listed in this definition. Examples of such medical events include allergic bronchospasm requiring intensive treatment in an emergency room or at home, blood dyscrasias or convulsions that do not result in inpatient hospitalization, or the development of drug dependency or drug abuse.

Events not to be considered as AEs/SAEs

Medical conditions present at the initial trial visit that do not worsen in severity or frequency

during the trial are defined as baseline medical conditions and NOT to be considered AEs.

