8.2. Classification of an Adverse Event

8.2.1. AE Severity Grade

Table 18 Adverse Event Severity Grading

Severity (Toxicity Grade)	Description
Grade 1	Mild: events require minimal or no treatment and do not interfere with the participant's daily activities.
Grade 2	Moderate: events result in a low level of inconvenience or concern with the therapeutic measures. Moderate events may cause some interference with functioning.
Grade 3	Severe: events interrupt a participant's usual daily activity and may require systemic drug therapy or other treatment.
Grade 4	Life threatening or disabling: patient at risk of death at the time of the event.
Grade 5	Death related to AE

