8.2.2. Severity of Adverse Events

The Cancer Therapy Evaluation Program (CTEP) Active Version of the NCI Common Terminology Criteria for Adverse Events (CTCAE 4.0) will be utilized for Adverse Event (AE) reporting. The CTEP Active Version of the CTCAE is identified and located on the CTEP website at: http://ctep.cancer.gov/protocolDevelopment/electronic_applications/ctc.htm All appropriate treatment areas should have access to a copy of the CTEP Active Version of CTCAE. If a particular AE's severity/intensity is not specifically graded by the guidance document, the investigator will revert to general definitions of grade 1 through grade 5 and use his or her best medical judgement.

Evaluation of an Adverse Event (AE):

- **Definitely Related** – A clinical event follows a reasonable temporal sequence from the time of Investigational Product (devimistat) administration, cannot be reasonably explained by other factors such as the subjects medical condition, or concurrent medical condition, or concurrent medication(s) AND either occurs following active Investigational Product (devimistat) administration, improves on stopping the Investigational Product (devimistat), or reappears on re-exposure
- **Probably Related** – A clinical event follows a reasonable temporal sequence from the time

of Investigational Product (devimistat) administration. The toxicity cannot be reasonably explained by other factors such as the subjects clinical state or concurrent medical condition, or concurrent medication(s)

- **Possibly Related** – A clinical event follows a reasonable temporal sequence from the time of active Investigational Product (devimistat) administration but could also have been produced by other factors such as the subjects clinical state, or concurrent medical condition, or concurrent medication(s)
- **Unlikely Related** – A clinical event is doubtfully related to active Investigational Product (devimistat). The event was most likely related to other factors such as the subject's clinical state, or concurrent medical condition, or concurrent medication(s) or the temporal relationship to the administration and/or exposure suggests that a causal relationship is unlikely
- **Not Related** - The event is clearly due to causes other than the Investigational Product (devimistat)

List of adverse events (AEs) for devimistat:

Definitely Related to devimistat:

- Hyponatremia
- Hyperglycemia
- Lymphocyte Count Decrease

Probably related to devimistat:

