8.4. Reporting Procedures

8.4.1. Adverse Event Reporting

At each visit the subject will be queried on changes in his/her condition. During the reporting period of the trial any untoward changes in the subject's condition will be recorded as AE, whether reported by the subject or observed by investigator.

Any treatment-emergent abnormal laboratory result which is clinically significant (defined as meeting one or more of the below must be documented on the CRF.

1. Accompanied by clinical symptoms
2. Leading to a change in study medication (e.g., dose modification, interruption or permanent discontinuation)
3. Requiring a change in concomitant therapy (e.g., addition of, interruption of, discontinuation of, or any other change in a concomitant medication, therapy or treatment)

It is the responsibility of the investigator to document all AEs that occur during the study. AEs should be reported on the appropriate page of the CRF. AEs should be reported for their actual grade and duration. The severity of the AE will be graded according to the NCI CTCAE Grading Scale (Current version).

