9.3. Analysis Populations

The following populations will be defined for the statistical analysis:

- The intent-to-treat (ITT) population includes all randomized subjects in the treatment arm they were allocated to
- The Per Protocol (PP) population consists of randomized subjects who do not have any major protocol violation and received at least one dose of study treatment
- The safety population consists of all subjects who received at least one dose of study treatment and have at least one post-baseline safety assessment

The ITT population will be used for all analyses of efficacy and baseline characteristics. The PP population will be used as a sensitivity analysis for efficacy endpoints. The safety population will be used for safety analyses.

Every effort will be made to keep all randomized patients in the study regardless of their adherence to treatment. Patients who stop their therapy for any reason will be followed until confirmed disease progression and/or death.

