5.2.3 Safety Population

The safety population consists of all randomized subjects who received at least one dose of study treatment, analyzed according to the treatment received. The safety population will be used for safety analyses.

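### The protocol's severe-toxicity outcome stops at grade 4, so a patient whose only severe event is fatal does not count on it; separately, protocol and SAP define the safety population differently

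*Protocol*

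**What the plan says.** **Severity outcome.** Protocol 9.4.4, and the safety objective in section 3, name three outcomes. The list begins "The safety outcomes will include the occurrence of at least one serious adverse event" and goes on "of at least one grade 3/4 adverse event, and of at least one adverse event requiring the discontinuation of study treatment".

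**Grading scale.** Protocol 8.2.1 (Table 18) has five grades. Grade 5 stands apart from grades 3 and 4: "Death related to AE". SAP 6.3.3 repeats the same five-grade table.

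**SAE definition.** The first criterion in protocol 8.1.2 is "Results in death".

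**Safety population.** Protocol 9.3 takes subjects who "received at least one dose of study treatment and have at least one post-baseline safety assessment". SAP 5.2.3 takes "all randomized subjects who received at least one dose of study treatment, analyzed according to the treatment received", with no post-baseline condition.

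**CTCAE version.** Protocol 8.2.2 states "Common Terminology Criteria for Adverse Events (CTCAE 4.0) will be utilized for Adverse Event (AE) reporting", and sections 3 and 9.4.4 say version 4. Protocol 8.4.1 states "The severity of the AE will be graded according to the NCI CTCAE Grading Scale (Current version". SAP 6.3.3 says 4.0 but, like protocol 8.2.2, also calls it the Active Version and points to the CTEP website.

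**SAP reporting.** SAP 6.3.3 tabulates patients with AEs by severity and patients with SAEs. It also summarises the number and cause of deaths by arm in the ITT population. It names no summary of grade 3 or higher.

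**The concern.** The grade 3/4 rate is the only severe-event rate that either document defines. On its literal wording it is not monotone in harm: a patient whose single severe event moves from grade 4 to grade 5 changes from having an event to having none. If the share of such patients differs between arms, the comparison on this outcome shifts by that difference, in favour of the arm with more of them. The trial is open label and aims to support approval on safety as well as efficacy (protocol 2.2), so this rate is likely to be read as a headline toxicity figure.

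The protocol's safety population raises a related problem. Whether a treated patient has a post-baseline assessment depends on surviving long enough to have one. A death before any assessment would leave the numerator and denominator of all three protocol outcomes, including the SAE outcome that otherwise catches fatal events.

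The CTCAE wording is a lesser matter. Two sites could grade the same event under different versions, but the wording cannot remove a patient or a death.

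**Working it through.** There is no stated figure to reproduce, so the first step is to trace who is counted where.

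| Treated patient | Any-SAE outcome | Grade 3/4 outcome | SAP severity table | SAP ITT death summary |
|---|---|---|---|---|
| Grade 4 AE, later a fatal AE | yes | yes | yes | yes |
| Only severe AE is fatal, assessed after baseline | yes | **no** | yes, as grade 5 | yes |
| Fatal AE before any post-baseline assessment, protocol 9.3 population | **no** | **no** | not applicable (SAP population governs) | yes |
| The same patient, SAP 5.2.3 population | yes | **no** | yes, as grade 5 | yes |

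The gap is specific: the grade 3/4 column for fatal-only patients, plus the third row.

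**Size of the grade 5 gap.** The documents give no phase III rate of fatal-only patients. Assume 1% to 5% of 250 per arm:

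- 0.01 × 250 = 2.5, about 3 patients
- 0.05 × 250 = 12.5, about 13 patients

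SAP 5.1.1 gives 528 randomized, or 264 per arm. That yields 2.6 to 13.2, again about 3 to 13. If the fatal-only shares are g1 and g2, the between-arm difference is off by g1 − g2, which is zero when they are equal.

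**What phase I can say.** Protocol Table 5 reports no grade 5 events in 20 patients. The upper 95% limit is 1 − 0.05^(1/20) = 13.9% one-sided, or 1 − 0.025^(1/20) = 16.8% two-sided. So phase I does not exclude 1% to 5%. However, it bounds any grade 5 event, which is a larger group than patients with a grade 5 event and no grade 3/4 event. The same table counts 118 toxicities of grade 3 or above, or 118/20 = 5.9 per patient on average. Most patients with a fatal AE would probably also have a grade 3/4 record, so the low end of the range is more plausible.

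**Size of the population gap.** Assume 0% to 3% of an arm die of an AE before any post-baseline assessment: 0 to 0.03 × 250 = 7.5, about 8 patients. The upper end is probably far too high (see the objection).

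**How the two interact.** Let b be the share with a grade 3/4 AE, g the fatal-only share among assessed patients, and y the share dying before assessment. At the unfavourable end of the assumptions (b = 0.50, g = 0.05, y = 0.03):

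- protocol population, grade 3/4: b/(1 − y) = 0.50/0.97 = 0.515
- SAP population, grade 3/4: b = 0.500
- SAP population, grade 3 or higher: b + g + y = 0.580

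Using the SAP population alone does not repair the severity outcome, because those patients return to the denominator but still have no grade 3/4 event. The outcome wording has to change as well. At the favourable end (b = 0.50, g = 0.01, y = 0) the gap is 0.510 − 0.500 = 1 point.

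**The case against.** The strongest case against is that a reader might infer that the worst cases drop out of the safety comparison, and the documents do not support that. Every fatal AE is an SAE, so it counts in the first outcome of the very sentence at issue. That list is not exhaustive, and safety rests mainly on AE frequency by CTCAE grade. The SAP shows AEs on a scale that includes grade 5, tabulates SAEs, and reports all deaths with cause in the ITT population. Death from any cause is the primary endpoint. A regimen that turned severe events into fatal ones would look worse on all of these.

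On early deaths, protocol 9.1 leaves full methods to the SAP, whose safety population keeps every treated patient. The excluded patient is also improbable. Table 15 lists ECGs at 0.25 and 0.5 hours on Cycle 1 Day 1 in both arms, QTc is a named safety endpoint, and Day 3 ECGs and Day 7 or 8 laboratory tests follow. Protocol 9.3 does not say which assessment qualifies, but these may well. The SAP contents list a section on changes from the protocol that is not in the text available here, so it cannot be said that the difference is undeclared.

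On CTCAE, sections 3, 8.2.2 and 9.4.4 and the SAP agree on version 4 or 4.0. The amendment list records a return from version 5 to version 4. The phrase in 8.4.1 looks like a leftover.

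No hypothesis test or alpha attaches to the grade 3/4 outcome, and the assumed percentages have no source.

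Nearly all of this stands, and it limits the point without removing it. The SAE outcome pools deaths with any hospitalization. The death summary covers a trial that waits for about 335 deaths, so AE deaths can be seen there only through the cause breakdown. The SAP severity table does not say whether each patient is placed at the worst grade, so a grade 3-or-higher rate cannot be assumed to follow from adding its rows. The protocol's population rule is still written as it is.

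**Conclusion.** The point holds in a limited form, with medium confidence. Read literally, the protocol's severe-event rate omits patients whose only severe event is fatal. Its safety-population rule conditions on something that depends on outcome and differs from the SAP; the visible text does not reconcile the two. The CTCAE inconsistency affects grading consistency only.

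The effect is of unknown size and probably small. Under an assumed fatal-only share of 1% to 5%, the grade 3/4 outcome misses about 3 to 13 patients per arm. The low end is more likely because severe and fatal events overlap within patients. Loss of patients through the assessment condition arises only if the protocol definition is applied, and the Cycle 1 Day 1 schedule makes it rarer still. The documents do not support a conclusion that fatal toxicity is hidden: it remains visible in the SAE, severity and death reporting. The change is worth making because the wording can mislead and costs almost nothing to correct.

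**What to change.** 1. In protocol sections 3 and 9.4.4, replace the grade 3/4 wording with 'grade 3 or higher (including grade 5)'. Add that per-patient summary, by arm, to the table list in SAP 6.3.3.
2. In protocol 9.3, delete the post-baseline assessment condition so that the safety population matches SAP 5.2.3.
3. As housekeeping, name CTCAE version 4.0 in protocol 8.4.1, and drop the Active Version wording in protocol 8.2.2 and SAP 6.3.3.

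Items 1 and 2 should be made together, since neither alone gives a rate that counts every treated patient with a severe or fatal AE. The cost is a handful of wording changes and one added table. The only downside is that the reported severe-event rate may be slightly higher.
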